Research plan:

Central Venous Catheter vs Midline in Difficulty Access patient – A Randomized controlled clinical pilot trial – pilot-ACCESS- D

Content

Overview:.....	2
Introduction	3
Methods	4

Last revised: 20 February 2025

EPM:

First: Dnr 2024-02365-01, Approved 22 April 2024

Second: Dnr 2024-05700-01, Approved 18 September 2024

CIP-kod: CVMID

CIV-ID: CIV-24-08-048798

ClinicalTrials.gov ID: NCT06719869

Overview:

Title:

1. Midline vs. Central Venous Catheter for Difficult Venous Access patients (ACCESS-D study) – A pilot trial

Study method: Randomized controlled clinical pilot trial

Purpose: To examine the feasibility of the ACCESS-D trial.

Population: 18+ age difficult intravenous access patients with expected 4-29 days of catheter dwell time in Ryhov Hospital, identified through the Acute care and Trauma unit (ATE).

Abbreviations:

CVC – Central venous catheter

DIVA – Difficult intravenous access

PICC – Peripherally inserted central catheter

PVC – Peripheral venous catheter

RCT – Randomized controlled clinical trial

USG – Ultrasound guided

VAD – Vascular access device

Introduction

Intravenous access is a necessity for nearly all inpatient medical care. Approximately half of hospitalized patients require a peripheral venous catheter (PVC), either to enable administration of medications intravenously or to repeatedly draw blood samples (1). Establishing a venous access sometimes requires repeated attempts, resulting in multiple needle sticks and prolonged discomfort for patients. In addition, this may lead to a diminished healthcare experience and create a stressful situation for both patients and healthcare personnel (2, 3). Delays in establishing intravenous access can result in setbacks in sample collection and drug administration (4, 5).

Difficult Intravenous Access (DIVA) is a situation that arises “when two or more clinicians fail two or more times to establish a peripheral access using conventional techniques, when a patient lacks visible or palpable veins or the patient has a stated or documented history of DIVA” (6). The prevalence of DIVA varies from 6% to 88% in different studies, primarily due to variations in definition of DIVA. Known risk factors are diabetes, intravenous drug abuse, sex (higher risk for women), chronic illness, obesity, malnutrition, absence of visible or palpable veins (7, 8). Although it is possible to establish a short, standard-length PVC through the help of ultrasound-guidance, this approach has limited scientific support (4, 9-11). In addition, ultrasound-guided PVCs are not health economically justifiable (12).

There are a handful of alternatives in terms of vascular access devices (VAD) for DIVA patients: Standard short PVC, Midline catheter, Central Venous Catheter (CVC) and Peripherally Inserted Central Catheter (PICC). A Midline is a long (8-12 cm), peripherally inserted venous catheter that is most commonly inserted into the upper arm via the basilic, cephalic or brachial veins, with its tip terminating below the level of the axilla (13). A Central Venous Catheter (CVC) is inserted through one of several veins (subclavian, jugular, or femoral) and terminates in a central vein, typically the superior vena cava, right atrium, or the iliac/inferior vena cava, depending on the insertion site. A PICC is an extended venous catheter inserted peripherally, similar to the Midline, inserted through the veins of the upper arm. However, the PICC terminates centrally, in the superior vena cava. There is some existing evidence supporting that Midline catheters could be safer compared to PICCs in short term (14-16). Today, CVCs are standard of care in many centers, but retrospective data indicate that Midlines could be a feasible option in DIVA patients (17). Furthermore, CVC insertion involves certain risks, such as arterial puncture, hematoma or pneumothorax (18). For DIVA patients in need of venous

access for 5 days or more, Midlines are preferred as per the Michigan Appropriateness Guide for Intravenous Catheters (MAGIC) guidelines (13). However, there are no randomized controlled clinical trials comparing Midlines to CVCs in DIVA patients.

Primary aim of study

The aim of the study is to test the feasibility of the study protocol before a future large-scale RCT.

Methods

CONSORT Methods

This pilot trial is a randomized, controlled, two-armed study with a sample size of 30 patients. A sample size of 30 is chosen as a convenience sample. The study will be conducted in Ryhov county hospital, in southern Sweden. Hospitalized patients across adult somatic wards with difficult intravenous access, are screened for potential trial recruitment. Patients are identified when staff from the ward contact the vascular access nurse. All inclusion and exclusion criteria are presented in Table 1. Patients identified, screened, and deemed eligible will be approached with study information. The trial is planned in accordance with the CONSORT guidelines for pilot trials (19).

Table 1 Inclusion and exclusion criteria

Inclusion Criteria	Exclusion Criteria

• Age 18 and over• DIVA criterium fulfilled;
○ 2 attempts of venous access by 2 cliniciansOR○ No visible nor palpable veinsOR○ History of difficult venous access• 4 - 29 days of catheter dwell time anticipated as assessed by referring clinician.	
• Unable to speak Scandinavian• Cognitive Impairment• Is to receive hyperosmolar solutions (600 milliosmoles/L or above).• Is to receive chemotherapy

Setting

The patient flowchart, depicted in Figure 1, outlines the vascular access procedures at Ryhov County Hospital. This process involves collaboration between a ward nurse and an anesthesia (vascular access) nurse. In case the ward nurse encounters difficulties in establishing venous access, patients are referred to the anesthesia nurse accordingly.

[figure not shown]
The insertion of catheters occurs in a dedicated post-op area. Clinicians in this setting have the option to choose between establishing a Midline catheter guided by ultrasound or opting for a Central Venous Catheter (CVC), also guided by ultrasound (USG).

Recruitment, Randomization and Blinding

Patients are assessed by the vascular access clinician in the Post-op ward. The recruitment process takes place in collaboration with anesthesiologists from the Acute Care and Trauma unit. Written consent and information are obtained by the physician. Subsequently, patients are randomized by the trial clinician using StudyRandomizer (<https://www.studyrandomizer.com>). Due to the visible nature of the intervention, blinding is not feasible. Trial participants are randomized in a 1:1 ratio using a block size of 6.

Patient identification, screening, and recruitment are outlined in Figure 1. After obtaining written consent, randomization, allocation and insertion of the VAD, patients return to their respective wards.

Figure 1: Flowchart of screening, assessment, recruitment and allocation in study.

Intervention, Midline:

Patients in the intervention group receive a 10 cm PowerGlide Pro™ Midline Catheter (Becton Dickinson). Catheters are inserted with ultrasound-guidance by an anesthesiologist using sterile gloves, mask, and large drape. The insertion site is treated with a solution of 0.5% chlorhexidine (wt/vol) in 70% alcohol (SCHA) and allowed to dry for 1 to 2 minutes prior to insertion. No prophylactic antibiotics are given as per default. All catheters are secured with using a

StatLock™ Stabilization device (Becton Dickinson), and the site is dressed with a semipermeable dressing (Tegaderm HP; 3M Healthcare, St. Paul, MN). A red paper tag is attached to the catheter, indicating study participation. Choice of insertion site on arm below or above the elbow avoiding catheter across joints and at the clinician's discretion.

Control, Central Venous Catheter (CVC):

Patients in the control group receive a Celsite 320 or 315 (B. Braun) or Pressure Injectable Arrowg+ard Blue Plus+ (Arrow). Catheters are inserted with ultrasound-guidance by an anesthesiologist with maximal sterile precautions (cap, mask, gown, gloves, and large drape) using the Seldinger technique. The insertion site is treated with a solution of 0.5% chlorhexidine (wt/vol) in 70% alcohol (SCHA) and allowed to dry for 1 to 2 minutes prior to insertion. No prophylactic antibiotics are given as per default. Catheters are secured with monofilament sutures, and the site is dressed with a semipermeable dressing (Tegaderm HP; 3M Healthcare, St. Paul, MN). A red paper tag is attached to the catheter, indicating study participation. The choice of insertion site is at the clinician's discretion.

Catheter care

Catheters (Midline and CVC) are controlled daily by the ward nurse. Control includes inspection of dressing, puncture site, the catheter itself and tags. The catheter function is assessed and flushed with minimum 20mL saline solution daily and in conjunction to use. For CVCs dressing is replaced every third day or earlier if necessary. Extension tubing, three-way connectors and injection valves are replaced every third day or earlier if necessary. With Midline, StatLock™ Stabilization device is replaced every 7th day or earlier if necessary.

Outcomes

The main outcomes are related to feasibility. Feasibility is defined as eligibility (>50% of screened patients considered eligible), recruitment (>70% of eligible patients consent to partake in trial), retention and attrition (<10% of patients lost to follow up, including those who withdrew consent), adherence (>80% of enrolled patients receive their randomized intervention), missing data (<10% of enrolled patients data missing) and venipuncture attempts (<20% of enrolled patients receive 2 venipunctures per insertion).

The secondary outcomes are insertion time and dwell time measured in minutes and days respectively. Catheter complications (infection, thrombosis and mechanical failure) are measured by objectively through bacterial culture, radiology and clinical expertise as per

standard clinical routine. Catheter complications during insertion and reason for removal are also registered during follow-up.

Follow-up

Follow-up will be performed in-ward every Monday and every Thursday by a research nurse or research assistant. Follow-up will be performed until the catheter is removed or until 28 days. Patients who are discharged from hospital with their catheter in situ will be followed through telephone interviews and chart reviews of out-patient notes

Ethical considerations

Ethical approval from the Swedish Ethical Review Authority is mandatory prior to trial start. The trial will be carried out in accordance with the study protocol under the principles of the Helsinki Declaration. The trial and study protocol will be prospectively registered on www.clinicaltrials.gov.

Regardless of whether a patient participates in the study, the need for venous access remains. Both midline catheters and CVCs are well-established methods for securing venous access, and the study presents no significant disadvantages or ethical concerns associated with their implementation.

Participation in the trial is entirely voluntary and is based on informed and signed consent. Participants have the right to withdraw their consent at any time for any reason, without prejudice to their medical care. Comprehensive oral and written information about the trial will be provided to participants before obtaining their consent and before their inclusion in the study. The research material will be stored in a secure safe where the research team have exclusive access.

Statistical analysis

Descriptive statistics are used to outline patients' baseline characteristics. For measurements that follow a normal distribution, group differences will be assessed using Student's t-test. Given the small sample size of 30, Mann-Whitney U test will be used to calculate differences in dwell time and insertion time between groups.

Funding

[name] has 25% part-time research funded by RJL and LiU.

Time plan (revised December 2024):

2024 Q1: Protocol construction

[figure not shown]
2024 Q2: Protocol submitted to Ethics Review Board

2025 Q1: Study start (January 13)

2025 Q2: Data analysis and manuscript

Results

Figure X: Patient flowchart according to CONSORT.

References

5. Witting MD. IV Access Difficulty: Incidence and Delays in an Urban Emergency Department. *The Journal of Emergency Medicine*. 2012;42(4):483-7.

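### The single, published block size of 6 in this open-label, one-hospital pilot makes on average 7.5 of 30 allocations certain to anyone who knows the size and tracks the sequence (minor)

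*Protocol*

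**What the plan says.** Under Recruitment, Randomization and Blinding, the Protocol states: "Trial participants are randomized in a 1:1 ratio using a block size of 6". It mentions neither stratification nor varying block sizes, nor any step to keep the size from recruiting staff. The same section says: "Due to the visible nature of the intervention, blinding is not feasible".

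The steps to enrolment are spread over several roles:

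- Referral (Methods, CONSORT Methods): "Patients are identified when staff from the ward contact the vascular access nurse".
- Expected duration (Table 1): "4 - 29 days of catheter dwell time anticipated as assessed by referring clinician".
- Assessment: "Patients are assessed by the vascular access clinician in the Post-op ward". Anesthesiologists take part in recruitment, and they also insert the catheters in both arms.
- Consent: "Written consent and information are obtained by the physician".
- Allocation: "Subsequently, patients are randomized by the trial clinician using StudyRandomizer".
- Place (Setting): "The insertion of catheters occurs in a dedicated post-op area". Clinicians there may otherwise choose either device.

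The sample size is 30 in two arms at one hospital. Ethical considerations says that the protocol will be registered publicly.

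**The concern.** With a known block size and visible past allocations, the end of each block can be deduced. The deduction needs no access to the randomisation list. It is available before eligibility is judged and before consent is sought, so a web service used after consent does not block it. A clinician who prefers one device for a given patient could decide whether to approach that patient, knowing which arm comes next. A patient who is not enrolled can still receive either device.

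If such foreknowledge were used, it could affect the eligibility and recruitment rates, which are main feasibility outcomes with targets of more than 50% and more than 70%. It could also affect the Mann-Whitney comparisons of insertion time and dwell time. The pilot tests the procedures for a larger RCT, where the same scheme would matter more.

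**Working it through.** **Inputs (Protocol).** Block size 6 and ratio 1:1, so 3 Midline and 3 CVC per block. With 30 patients there are 30/6 = 5 complete blocks. No stratification is stated, so I assume one sequence. The Protocol gives no predictability figure to reproduce.

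**Certain allocations, fixed blocks of 6.** There are C(6,3) = 20 equally likely orderings. An allocation is certain once one arm has used its 3 places.

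- 12 orderings have 1 certain allocation, 6 have 2, and 2 have 3.
- Mean per block: (12×1 + 6×2 + 2×3)/20 = 30/20 = 1.5.
- Check by position: the 4th place is certain with probability 1/10, the 5th with 2/5 and the 6th always; 0.1 + 0.4 + 1 = 1.5.
- Over 5 blocks: 5 × 1.5 = 7.5 of 30 (25%), minimum 5, maximum 15.
- Convolving the five blocks gives P(5 to 10 certain) = 0.0778 + 0.1944 + 0.2592 + 0.2268 + 0.1431 + 0.0672 = 0.968.

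**Best guess, fixed blocks of 6.** Guess the arm with more places left. The expected correct guesses at places 1 to 6 are 0.5, 0.6, 0.6, 0.7, 0.7 and 1.0, which sum to 4.1 per block. Over 5 blocks that is 20.5 of 30 (68.3%), against 15 by chance.

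**Varying blocks.** Here the observer knows the set of sizes, tracks every allocation and updates the probability of each possible current block. Equal probabilities for the sizes are my assumption. The values come from an exact recursion over 30 patients.

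| Sizes | Certain | Predictable ≥80% | ≥85% | ≥90% | Best guess correct |
|---|---|---|---|---|---|
| 6 (as planned) | 7.5 | 7.5 | 7.5 | 7.5 | 68.3% |
| 4, 6 | 1.7 | 8.5 | 5.5 | 2.7 | 68.8% |
| 2, 4, 6 | 1.2 | 14.9 | 4.9 | 2.0 | 69.9% |
| 4, 6, 8 | 0.7 | 6.5 | 3.0 | 1.4 | 67.5% |

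A simulation of 60,000 sequences for 4, 6 and 8 agrees (0.708 certain, 6.517 at 80% or more, 67.5%).

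Two things follow. Varying the sizes removes near-certainty but hardly changes the best-guess rate, and sets with small blocks make moderate predictability worse. Hiding the sizes as well removes certainty altogether, because an observer who does not know the largest size can never be sure. It does not lower the best-guess rate: the best guess is always the arm with fewer patients so far, which needs no knowledge of the sizes.

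**Balance.** With 4, 6 and 8 and a stop at 30 patients, the split is 15:15 in 72.4% of sequences, 16:14 in 27.3% and 17:13 in 0.3%. Fixed blocks of 6 always give 15:15.

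**If enrolment has begun.** Certain allocations among the patients still to be randomised:

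| Patients left | Fixed 6 | 4, 6, 8 |
|---|---|---|
| 30 | 7.5 | 0.7 |
| 24 | 6.0 | 0.6 |
| 18 | 4.5 | 0.4 |
| 12 | 3.0 | 0.3 |
| 6 | 1.5 | 0.06 |

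**The case against.** A fixed permuted block with web randomisation after consent is a valid and common scheme, and nothing in the Protocol contradicts it. The risk needs someone who knows the size, follows every allocation and has discretion over entry. The Protocol shows no such person. Ward staff start the referral, the referring clinician judges expected dwell time, and assessment, consent and randomisation are described under separate roles. Someone inclined to steer does not need certainty, and on the best-guess measure the gain from 4, 6 and 8 is about 0.25 of 30 allocations (20.5 against roughly 20.25). The main outcomes are feasibility rates, not arm comparisons, and the sample of 30 was chosen for convenience. The change would probably fall in the middle of enrolment.

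Most of this stands, and it is why the point is minor. Split roles narrow the room for steering mainly to the post-op assessment and the consent approach, but they do not close it; the roles may also overlap. The small change in the best-guess rate is real. The case for change rests on removing certain and nearly certain allocations: at 90% or more, the number falls from 7.5 to 1.4.

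**Conclusion.** The concern holds as a minor design point. With the scheme as stated, on average 7.5 of 30 allocations (25%) are knowable in advance. This rests on one unstratified sequence of five complete blocks and an observer who knows the size and tracks every allocation. Unstated stratification or incomplete blocks would change the number. The document shows no misuse, and neither the direction nor the size of any resulting bias can be derived from it. The point is worth acting on because the remedy is cheap and the scheme may be carried into the RCT.

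**What to change.** Use randomly varying block sizes without size 2, for example 4, 6 and 8. State in the Protocol only that block sizes vary, and keep the sizes in a document that recruiting staff cannot see.

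Before enrolment this costs one setting in the randomisation list and one sentence, plus the loss of a guaranteed 15:15 split. After the start it means changing a live list from the next block, with any amendment handling; the Protocol does not show whether the randomisation service allows this. Timing matters: the start was planned for 13 January 2025, the last revision is dated 20 February 2025, and analysis was planned for 2025 Q2. If few patients remain, leave the list as it is, report the fixed, disclosed block size as a limitation, and specify varying, concealed blocks for the later RCT.

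### Apart from baseline descriptives, the Statistical analysis section fixes only between-arm significance tests; for the two secondary time outcomes, estimates with confidence intervals would serve this pilot better

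*Protocol*

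**What the plan says.** The protocol's aim is feasibility: "The aim of the study is to test the feasibility of the study protocol before a future large-scale RCT". On size it says "A sample size of 30 is chosen as a convenience sample", and on allocation "Trial participants are randomized in a 1:1 ratio using a block size of 6".

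Under Outcomes, "The main outcomes are related to feasibility". Six criteria follow, each with a numerical threshold, for example "eligibility (>50% of screened patients considered eligible" and "recruitment (>70% of eligible patients consent to partake in trial". Insertion time (minutes) and dwell time (days) are named as secondary outcomes.

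The Statistical analysis section has three sentences. The first assigns descriptive statistics to baseline characteristics. The second reads "For measurements that follow a normal distribution, group differences will be assessed using" Student's t-test, and names no variable. The third gives the small sample as its reason and says that the "Mann-Whitney U test will be used to calculate differences in dwell time and insertion time between groups". The section states no significance level, effect size or power.

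**The concern.** Two things in the wording do not fit together.

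- **The named method does not yield the named quantity.** The Mann-Whitney test is said to calculate differences in the two times. It produces a rank statistic and a p-value. A difference in minutes or days needs an estimator, and none is named.
- **The t-test has nothing assigned to it.** The only outcomes that the protocol defines as continuous are insertion time and dwell time, and both go to Mann-Whitney. The t-test sentence is left without a stated target.

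Behind these lies the choice of method. This is a small sample, not sized for a comparison, and the arm comparison is fixed as significance tests. With so few patients a non-significant p-value fits both no difference and a large one, and the section does not label the comparison exploratory. What is at stake is how the two secondary time outcomes will be read, not the feasibility decision.

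**Working it through.** **Inputs from the protocol.** Total sample 30, a convenience sample (CONSORT Methods). Allocation 1:1 in blocks of 6 (Recruitment, Randomization and Blinding). Follow-up until removal or 28 days (Follow-up). Anticipated dwell 4 to 29 days (Table 1).

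**Assumptions, because the protocol gives no figures.** Two-sided 5% level. True shifts of 0.5, 0.8 and 1.0 SD as a range. Log-normal dwell time with log-SD 0.8 as one skewed example.

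**Step 1, patients per arm.** 30/6 = 5 complete blocks, so 30/2 = 15 per arm. The protocol does not print this figure. The total of 30 rests on no calculation, so there is no power figure to reproduce.

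**Step 2, power of the planned Mann-Whitney test, 15 v 15.**

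| True shift | Simulated (5,000 runs) | t-test approximation with n x 0.955 |
|---|---|---|
| 0.5 SD | 24% | 25% |
| 0.8 SD | 52% | 54% |
| 1.0 SD | 73% | 73% |

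The factor 0.955 is the efficiency of the Mann-Whitney test relative to the t-test under normality. By the same approximation, 80% power needs a true shift of about 1.09 SD.

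**Step 3, skewed data.** The test depends only on ranks, so a log-normal median ratio R acts as a shift of ln(R)/0.8 SD on the log scale. For R = 1.5 this is 0.405/0.8 = 0.51 SD, with simulated power 25%. For R = 2.0 it is 0.693/0.8 = 0.87 SD, with simulated power 59%. These agree with Step 2.

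**Step 4, what an interval would show.** The half-width of a 95% confidence interval for a mean difference is t(0.975, 28) x sqrt(2/15) = 2.048 x 0.365 = 0.75 SD. An observed difference of zero would be compatible with true differences of up to about 0.75 SD in either direction. The interval puts this on the page; the p-value does not.

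**Step 5, which outcomes the tests touch.** The six feasibility criteria are proportions compared with fixed thresholds. Neither the t-test nor Mann-Whitney applies to them, and neither is needed to judge them. The tests bear on insertion time, dwell time and whatever the t-test sentence was meant to cover.

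**Step 6, dwell time at the end of follow-up.** Follow-up ends at removal or at 28 days, and the anticipated dwell runs to 29 days. A catheter still in place at 28 days has an unknown full dwell time. Any summary or difference for dwell time must therefore say that it counts days only up to 28.

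**The case against.** The case on the other side is substantial and narrows the point.

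- **Feasibility is not left to the tests.** A reader might infer that significance tests are the only analyses fixed and that the feasibility aim goes unanswered. The protocol does not support that. It assigns descriptive statistics to baseline, and the Outcomes section settles feasibility by thresholds that need no test.
- **Baseline testing is not stated.** Because the t-test sentence follows the one on baseline, a reader might infer that baseline differences will be tested, which is uninformative after randomisation. That is one possible reading. Another is a general default, overridden for the two times because the sample is small. What stands is that the sentence has no named target. Any figure for chance baseline findings would need a number of baseline variables, and the protocol lists none, so I rely on no such figure.
- **The planning use is inferred.** The protocol looks ahead to a large trial but does not say that the pilot will supply an effect size or SD. With a half-width of 0.75 SD, an effect estimate would be a weak basis for planning anyway. The case for an interval is honest reporting.
- **Estimates could sit in an analysis plan.** Their absence alone would be no finding, and Mann-Whitney is a defensible test for skewed times in a small sample. Naming it does not forbid medians and intervals. The point that remains is about what the protocol does fix: a test described as delivering a difference, and a second test with no target.
- **No decision hangs on these p-values.** This is correct, and it is why the severity is low.

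**Conclusion.** The point holds in limited form. Apart from baseline descriptives, the Statistical analysis section fixes only between-arm significance tests, on an unpowered sample of 15 per arm. The Mann-Whitney sentence promises a quantity that the test does not give, and the t-test sentence has no stated target.

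Power is about one in four for a 0.5 SD shift and stays below 80% even at 1.0 SD, so a p-value by itself would carry little information. These figures assume a two-sided 5% level, the stated range of shifts and all 30 patients contributing data; fewer would lower them.

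The feasibility outcomes, their thresholds and the conduct of the trial are unaffected. This is a cheap improvement of low severity, confined to the two secondary time outcomes and the wording around them.

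**What to change.** Change the Statistical analysis section as follows.

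1. Delete the Student's t-test sentence.
2. State that baseline characteristics are summarised by arm without significance tests.
3. Replace the Mann-Whitney sentence with wording such as: *Insertion time and dwell time are summarised by arm as median and interquartile range, with the Hodges-Lehmann difference between arms and its 95% confidence interval. These comparisons are exploratory, and no claim of a difference or of no difference is based on them.*
4. Define the dwell-time outcome as days with the catheter in place up to 28, and report by arm how many catheters were still in place at 28 days.

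The cost is a few sentences of protocol wording and no extra data. The downside is that the pilot report carries no headline p-values for the arm comparison.

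### Does comparing all-cause dwell days by a Mann-Whitney test, without using the recorded reason for removal, call for a change to the plan?

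*Protocol*

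**What the plan says.** Under Outcomes, the Protocol sets the main outcomes as feasibility criteria and then adds: "The secondary outcomes are insertion time and dwell time measured in minutes and days respectively". Neither an end event nor a removal cause is attached to dwell time. All-cause days is therefore an inference, but it is the only reading the text supports.

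The same section lists catheter complications as measured separately and adds: "Catheter complications during insertion and reason for removal are also registered during follow-up". Under Follow-up: "Follow-up will be performed until the catheter is removed or until 28 days".

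The Statistical analysis section fixes the comparison, that a "Mann-Whitney U test will be used to calculate differences in dwell time and insertion time between groups", and introduces it with the words "Given the small sample size of 30". It gives the removal reason no role in that test. It does not rule out other summaries.

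Three other statements bear on the point. Table 1 admits patients with "4 - 29 days of catheter dwell time anticipated as assessed by referring clinician". The retention criterion is "retention and attrition (<10% of patients lost to follow up, including those who withdrew consent". The section on recruitment and randomization states: "Due to the visible nature of the intervention, blinding is not feasible".

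**The concern.** Dwell time mixes two processes: how long the patient needs access, and how long the catheter works. Patients enter on anticipated need, so many catheters will come out because the need has ended. A rank test on days treats a completed course ending on day 6 and a failure on day 6 as the same result.

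Two misreadings would follow if dwell time were taken as device performance. A real difference in failure could be diluted by end-of-therapy removals, and a non-significant result taken to mean similar devices. Conversely, if one device were removed electively sooner than the other, dwell could differ without any difference in failure. Staff know the allocation, so the second case is conceivable. Because the pilot prepares a large trial, an ambiguous endpoint might be carried forward.

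A lesser worry is that a rank test has no proper place for patients lost before removal. It must drop them or treat their last known day as a removal day.

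**Working it through.** The Protocol gives no significance level, power, effect size or failure rate for dwell time, so there is no figure of its own to reproduce.

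**Inputs from the Protocol.** There are 30 patients, allocated 1:1 in blocks of 6, hence 15 per arm. Anticipated dwell is 4 to 29 days, follow-up runs to removal or day 28, and losses must be below 10%.

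**Early losses.** 10% of 30 is 3, so meeting the criterion means 0, 1 or 2 patients lost. Catheters still in place at day 28 can share the top rank, which a Mann-Whitney test handles without difficulty.

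**A constructed example.** Give both arms the same 15 dwell values, with 6/15 against 1/15 removed for failure. Identical values force p = 1.0. The failure difference is 0.400 − 0.067 = 0.333. The Wilson limits are 0.198 to 0.643 for 6/15 and 0.012 to 0.298 for 1/15. Newcombe's interval is then:

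- lower: 0.333 − √[(0.400 − 0.198)² + (0.298 − 0.067)²] = 0.333 − 0.307 = 0.026
- upper: 0.333 + √[(0.643 − 0.400)² + (0.067 − 0.012)²] = 0.333 + 0.249 = 0.582

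Fisher's exact test on the same table gives p = 0.08. One failure fewer (5/15 against 1/15) gives 0.267, with interval −0.028 to 0.522. The example shows that dwell and failure are different quantities. It also shows how little 15 per arm says about failure.

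**Simulation.** All inputs in this step are assumptions: therapy need lognormal with underlying median 6, 8 or 12 days and sigma 0.6, kept to 4 to 29 days; constant failure hazards; whole-day dwell; two-sided 5% tests; 3,000 pilots per setting. Ranges run over the three medians, with the midline hazard first.

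| Failure hazard per day | Mann-Whitney rejects | Midline median dwell ≥ CVC median | Mean total failures |
|---|---|---|---|
| 0.02 vs 0.02 | 4–5% | – | – |
| 0.03 vs 0.01 | 8–10% | 35–49% | 4.5–6.5 |
| 0.05 vs 0.01 | 15–26% | 19–38% | 6.2–8.5 |
| 0.08 vs 0.01 | 33–52% | 7–20% | 8.3–10.9 |

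The first row confirms validity. At 0.05 against 0.01, where 33 to 45% of midlines and 8 to 12% of CVCs fail, sensitivity is low.

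**Two checks on these figures.**

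- The third column counts ties. In a rerun at 0.05 against 0.01 with 1,500 pilots per setting, exact ties of whole-day medians were 22%, 14% and 10% of pilots, out of totals of 36%, 28% and 21%. That is 22/36 = 61%, 14/28 = 50% and 10/21 = 48%, so about half or more of the apparent reversals are ties.
- At 0.03 against 0.01, Fisher's test on failures rejects in 7 to 13% of the rerun pilots, against 7 to 10% for Mann-Whitney. For that contrast the limit is mainly the sample size.

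**The case for a change.** The strongest case for a change is that the ambiguity does not shrink with more patients. In a separate simulation with constant elective-removal hazards, take failure hazards of 0.06 and 0.02 per day and elective removal of 0.10 and 0.14, so that total removal is equal at 0.16. Then 37% of midlines and 12% of CVCs fail, yet Mann-Whitney rejects in only about 4% of pilots at 15 per arm and about 5 to 6% at 200 per arm. With equal failure hazards of 0.02 but elective removal at 0.10 against 0.20, it rejects in 27%. A pilot is a sensible place to settle an endpoint, and the data needed are already collected. A cause-specific log-rank test would also be more sensitive to failure: 40 to 55% rejection at 0.05 against 0.01, in the simulation with lognormal therapy need.

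What stands is that the dwell comparison follows total removal and must not be reported as evidence on failure. The rest carries less weight. The 4% and 27% results need elective removal to differ by device, and the Protocol gives no figure for that. The log-rank test addresses a different hypothesis and does not show the chosen test to be wrong. A cause-specific analysis would rest on about 5 to 11 events whose cause is assigned by unblinded staff, so it adds a classification risk that all-cause days largely avoid. Competing-event methods, handling of losses and removal-reason categories are also matters commonly left to a statistical analysis plan, which is not at hand here.

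**Conclusion.** The observation is accurate but does not call for a change. Followed as written, the plan gives a valid comparison of all-cause dwell, which is a legitimate secondary quantity that the Protocol does not label as device performance. Failure is covered separately through the recorded infections, thromboses, mechanical failures and removal reasons. A reader is left unable to tell early failure from early end of therapy only if dwell is reported without them, and nothing in the Protocol says it will be.

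The consequence is small. Dwell time is secondary, the 30 patients are a convenience sample, no power is claimed and no feasibility criterion uses dwell. Early losses touch at most 2 patients if the retention criterion is met. The quantitative case rests on assumed hazards and an assumed distribution of therapy need. It shows low sensitivity to a question that the test was not set to answer.

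Analysts can fill the gap in reporting: median and interquartile range of dwell by arm beside a table of removal reasons, with a note on how any early losses were counted. That is ordinary good practice and needs no amendment.
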